STUDY PROTOCOL

Official Title: Comparison of Bidirectional Palpation Test and Transit Time Flow Measurement for LIMA-LAD Graft Patency NCT Number: NCT06934993

Date: 11.10.2024

Sponsor Institution: Istanbul University-Cerrahpaşa, Faculty of

Medicine, Department of Cardiovascular Surgery

Ethics Approval: Approved by the Istanbul University-Cerrahpaşa Clinical Research Ethics Committee (approval dated 11.10.2024;

Turkish document added to the end of the file)

A. Rationale and Objective of the Study:

The aim of this study is to evaluate the correlation between the Bidirectional Palpation Test and TTFM measurements, and to assess early postoperative outcomes by examining graft patency using coronary CT angiography.

B. Main Study Form:

B.1.1. General Information:

Graft patency is one of the most critical factors determining morbidity and mortality after coronary artery bypass grafting (CABG). Revascularization of the left anterior descending (LAD) artery has been associated with improved long-term outcomes, including reduced mortality and relief of angina symptoms. The first-choice graft for LAD revascularization is the left internal mammary artery (LIMA). LIMA-LAD anastomosis is considered the gold standard due to its superior long-term patency.

Therefore, evaluating the patency of the LIMA-LAD anastomosis is crucial for both early and long-term outcomes. While various methods are used routinely, many are complex and costly. The bidirectional palpation test, developed in our clinic, is a subjective yet simple and reliable method. In this test, after completion of anastomoses, temporary weaning from cardiopulmonary bypass (CPB) is performed to establish pulsatile pressure. A segment of the LIMA with palpable pulse is identified. In the first step, a buildog clamp is placed distal to this point; continued palpation indicates antegrade flow from the subclavian artery. In the second step, the clamp is moved proximally; continued pulse detection indicates retrograde flow through the LIMA-LAD anastomosis, indirectly confirming its patency.

Additionally, Transit Time Flow Meter (TTFM) measurements will be used as an objective method to evaluate graft patency. This study aims to assess the correlation between the bidirectional palpation test and TTFM with postoperative graft patency determined by coronary CT angiography. Within the first 30 postoperative days, coronary CTA will evaluate patency of the LIMA and other grafts, graft-native vessel calibration, graft position, sternum healing, and lung parenchyma.

B.1.2. Materials and Methods

B.1.2.1. Subjects Inclusion Criteria:

Patients planned for CABG in our clinic will be informed and consented. Those undergoing LIMA-LAD anastomosis will be included.

Exclusion Criteria:

Patients at risk for contrast nephropathy and those undergoing LAD revascularization with grafts other than LIMA will be excluded.

B.1.2.2. Methods Used in the Study

a. Laboratory and Clinical Assessment Methods:

Bidirectional palpation and TTFM measurements will be conducted intraoperatively using standard techniques, posing no additional surgical risk. Coronary CTA is selected as it is a non-invasive imaging method used to assess native coronary arteries and graft patency post-revascularization.

b. Statistical Methods:

Chi-square test, Student's t-test, Fisher's exact test, and Kaplan-Meier survival analysis for primary endpoints.

C. Protocol: C.1. Start Date of the Study: April 15, 2024

C.2. Duration of the Study:

6 months

C.3. Study Location:

Istanbul University - Cerrahpaşa, Cerrahpaşa Faculty of Medicine, Department of Cardiovascular Surgery

C.4. Study Investigators:

Advisors:

[name]. [name] Dr. [name]

Principal Investigator:

Dr. [name]

D. Study Outcomes, Ethics and Legal Requirements:

D.1. Outcomes:

This study is expected to reduce morbidity and mortality due to graft occlusion by allowing intraoperative assessment of graft flow and anastomosis quality. Revising the graft during surgery, if necessary, may prevent the risks and burden of reoperation. Additionally, if the bidirectional palpation test results are consistent with TTFM and early graft patency is confirmed via coronary CTA, this cost-free and easily applicable method may gain broader clinical adoption.

D.2. Ethics Committee Notification:

All necessary ethics committee notifications are planned before, during, and after the study.

D.3. Data Storage and Quality Assurance:

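### Nothing requires the subjective palpation result to be recorded before the TTFM reading is seen, so the agreement between the two can be inflated.

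*Protocol*

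**What the plan says.** Section A makes the correlation between palpation and TTFM the first aim. Section B.1.1 says that palpation, a test which the clinic itself developed, "is a subjective yet simple and reliable method". It places the test late in the operation: "after completion of anastomoses, temporary weaning from cardiopulmonary bypass (CPB) is performed to establish pulsatile pressure". It then describes the two clamp steps, each ending in a judgement of whether a pulse can still be felt.

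The comparator follows in the same section: "Transit Time Flow Meter (TTFM) measurements will be used as an objective method to evaluate graft patency". The reference imaging comes after surgery: "Within the first 30 postoperative days, coronary CTA will evaluate patency of the LIMA and other grafts".

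On how the two intraoperative tests are obtained, section B.1.2.2, item a, says only: "Bidirectional palpation and TTFM measurements will be conducted intraoperatively using standard techniques, posing no additional surgical risk". The text at hand does not say which test comes first, who performs each, when the palpation result is fixed, or what the CTA reader knows.

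Section D.1 foresees broader clinical use "if the bidirectional palpation test results are consistent with TTFM and early graft patency is confirmed via coronary CTA".

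**The concern.** Agreement between two tests is informative only if each result is obtained without knowledge of the other. Here one of the two is, in the protocol's own words, a subjective judgement, made by the clinic that developed the test. If the operator has seen the TTFM value, a doubtful pulse can be called to match it, or palpation can be repeated until the two agree. Either would raise the agreement between palpation and TTFM, which is the first aim and one of the two conditions named in D.1.

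The order of recording is a rule of conduct. A statistical analysis plan, which may exist, can choose which patients or records to analyse. It cannot make a palpation call independent if the call was made after the reading was seen.

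**Working it through.** **Reading the text.** The protocol states no sample size, expected agreement or rate of abnormal findings, so there is no figure to reproduce. The check is whether any provision separates the two results.

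- B.1.1: palpation follows completion of the anastomoses, during temporary weaning. Its timing relative to TTFM is not given.
- B.1.1: TTFM is introduced after palpation, as an additional method. No order of performance is stated.
- B.1.2.2, item a: both are intraoperative and use standard techniques. Nothing is said on order, recording or masking.
- B.1.1: CTA takes place within 30 postoperative days. It always comes later and cannot influence palpation; only its reading could be influenced by the earlier results.

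A palpation call made or repeated after TTFM is therefore permitted as written.

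**Illustration of size.** Every input is an assumption. Let p be the proportion of grafts with abnormal TTFM, s the proportion of those called abnormal by independent palpation, q the proportion of TTFM-normal grafts called abnormal, and f the fraction of discordant palpation calls that move to match a known TTFM value. Then

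- s′ = s + (1 − s)f and q′ = q(1 − f)
- observed agreement Po = p·s′ + (1 − p)(1 − q′)
- palpation-abnormal proportion m = p·s′ + (1 − p)q′
- chance agreement Pe = p·m + (1 − p)(1 − m)
- kappa = (Po − Pe)/(1 − Pe)

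With p = 0.10, s = 0.50, q = 0.05:

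| f | s′ | q′ | Po | m | Pe | kappa |
|---|---|---|---|---|---|---|
| 0 | 0.500 | 0.0500 | 0.9050 | 0.09500 | 0.8240 | 0.0810/0.1760 = 0.460 |
| 0.10 | 0.550 | 0.0450 | 0.9145 | 0.09550 | 0.8236 | 0.0909/0.1764 = 0.515 |
| 0.25 | 0.625 | 0.0375 | 0.92875 | 0.09625 | 0.8230 | 0.10575/0.1770 = 0.597 |
| 0.50 | 0.750 | 0.0250 | 0.9525 | 0.09750 | 0.8220 | 0.1305/0.1780 = 0.733 |

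With p = 0.05 and the same s and q, kappa is 0.371, 0.507 and 0.655 at f = 0, 0.25 and 0.50.

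Over p = 0.03, 0.05 and 0.10, with s = 0.50 or 0.70 and q = 0.05:

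| f | kappa | raw agreement | apparent sensitivity against TTFM |
|---|---|---|---|
| 0 | 0.29 to 0.61 | 0.905 to 0.943 | 50% to 70% |
| 0.25 | 0.42 to 0.70 | 0.929 to 0.957 | 62.5% to 77.5% |
| 0.50 | 0.57 to 0.80 | 0.952 to 0.971 | 75% to 85% |

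The upward direction follows from the mechanism, because calls move only from discordant to concordant. The size follows wholly from the inputs chosen.

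**Dates.** Section C gives a start of April 15, 2024 and a duration of 6 months, which runs to mid-October 2024. The document is dated 11.10.2024. Read as day, month, year, that is a few days before the stated period ends.

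**The case against.** The strongest reply is that the point rests on silence, and that what order the text does suggest is the harmless one: palpation is described first, straight after the anastomoses, and TTFM is added afterwards. If practice follows that, only repeat palpation after TTFM remains as a route to bias, and the protocol describes no repeat palpation. A case form may also fix the sequence. This lowers the likelihood of bias but does not remove the gap: the order of description is not a rule of conduct, and no record is fixed before the TTFM value is known.

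The illustration has no basis in the documents, and kappa is not among the methods listed in B.1.2.2, item b. At 10% of discordant calls shifted, kappa moves only from 0.46 to about 0.52. That stands, and the figures should be read as showing how sensitive agreement is to such shifts, not as an estimate.

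Three stronger readings are tempting, and the documents do not support them.

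- *That bias pushes both the TTFM and the CTA comparison the same way.* If palpation and TTFM disagree, an unmasked CTA reader could lean towards either. A palpation call moved to match a wrong TTFM value would agree less with CTA. D.1's CTA condition is also confirmed patency, which is not the same as agreement between palpation and CTA.
- *That no later analysis can address the problem.* Where the order is on record, leaving out patients whose palpation followed TTFM addresses it in part.
- *That the trial would recommend replacing TTFM.* D.1 speaks only of possible broader adoption of palpation.

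Finally, with the stated dates, a rule for future operations may protect few patients. That stands, and it shapes the fix.

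**Conclusion.** The point holds for palpation against TTFM. The protocol makes their correlation its first aim, calls one test subjective and the other objective, and allows the subjective call to be made or repeated with the objective value known. The text shows a risk of inflated agreement, not that inflation occurred. Its size cannot be determined from the documents; on the assumed inputs it ranges from a few hundredths of kappa to more than a quarter (0.46 to 0.73). Masking the CTA reader is a secondary safeguard only, because the direction of any bias there is uncertain. The conclusion covers the protocol text at hand and assumes that no other study document fixes the order of recording. The change should be made: it protects the main comparison at almost no cost, although its value for new patients depends on how many operations remain.

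**What to change.** In section B.1.2.2, item a, add:

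1. The result of each palpation step (pulse present or absent) is recorded, with the time, before the TTFM reading is seen.
2. This first record is the one used in the agreement analysis. Any later palpation is recorded separately and does not overwrite it. Clinical use of either test is unaffected.
3. As a secondary safeguard, the usual CTA reader is not given the palpation or TTFM results when judging LIMA patency.

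For patients already operated on, report which test came first wherever the operative record shows it. Give agreement with and without those whose palpation followed TTFM or whose order is unknown, and state possible review bias as a limitation. Order should come from the record rather than from recall.

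The cost is a short amendment, one timed line on the case form, and a CTA request that leaves out the intraoperative findings. No extra patients, staff or procedures are needed. For past patients the cost is a review of the operative records, and the restricted analysis may be small if times were not charted.

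### CTA within 30 days is the only stated route to a patency status, so a LIMA-LAD failure proven before CTA by other means has no place in the definition

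*Protocol*

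**What the plan says.** Section B.1.1 sets out to relate palpation and TTFM to "postoperative graft patency determined by coronary CT angiography". The timing is a window with no fixed day: "Within the first 30 postoperative days, coronary CTA will evaluate patency of the LIMA and other grafts". Section B.1.2.2 (a) gives the reason for choosing CTA, namely that it is non-invasive, and names no other source of a patency status.

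Entry is settled by the operation, not by having a scan. In B.1.2.1: "Those undergoing LIMA-LAD anastomosis will be included". The exclusions are "Patients at risk for contrast nephropathy and those undergoing LAD revascularization with grafts other than LIMA will be excluded". Death, reoperation and absence of a CTA are not among them.

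The protocol also states what graft failure does to patients. B.1.1 opens with "Graft patency is one of the most critical factors determining morbidity and mortality after coronary artery bypass grafting". D.1 speaks of the aim to "reduce morbidity and mortality due to graft occlusion" and says "Revising the graft during surgery, if necessary, may prevent the risks and burden of reoperation".

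B.1.2.2 (b) lists Kaplan-Meier analysis for the primary endpoints. It defines neither the endpoint nor its event, so it does not supply the missing status.

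**The concern.** A patient whose LIMA-LAD graft occludes early may die, be taken back to theatre or have urgent angiography before the study CTA. The failure may then be proven beyond doubt, yet it was not determined by CTA, so the stated reference assigns it nothing. If the graft is repaired and CTA follows, the scan describes the repaired graft and the failure is still not recorded.

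On the protocol's own premise these losses are not random: occlusion is what leads to death and reoperation. A set of CTA results depleted of failed grafts shows a higher patency rate, and a normal intraoperative test appears to be followed by fewer failures. D.1 names early patency on CTA as one of two conditions for wider use of palpation, the other being consistency with TTFM. The gap therefore touches a result that the protocol intends to rely on.

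**Working it through.** The protocol gives no sample size, failure rate, accuracy target, death or reoperation rate, or CTA completion rate. There is no figure of its own to reproduce, and only direction and sensitivity to assumptions can be checked.

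**1. Direction.** Assumptions, none from the document: 1,000 patients; true failure 5%; sensitivity for failure 0.50; specificity 0.97; every patent graft scanned.

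- Failed grafts: 1,000 × 0.05 = 50, of which 25 flagged and 25 passed by the test.
- Patent grafts: 950, of which 950 × 0.97 = 921.5 passed and 28.5 flagged.

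Formulas, using grafts with a CTA status:

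- failure rate = failed / all
- predictive value of a normal test = patent passed / all passed
- predictive value of an abnormal test = failed flagged / all flagged
- agreement = (patent passed + failed flagged) / all
- sensitivity = failed flagged / all failed

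| Failures reaching the analysis | Failure rate | Normal test PV | Abnormal test PV | Agreement | Sensitivity |
|---|---|---|---|---|---|
| All (25 passed, 25 flagged) | 50/1000 = 5.0% | 921.5/946.5 = 97.4% | 25/53.5 = 46.7% | 946.5/1000 = 94.65% | 25/50 = 0.50 |
| Half of all lost (12.5, 12.5) | 25/975 = 2.6% | 921.5/934 = 98.7% | 12.5/41 = 30.5% | 934/975 = 95.8% | 12.5/25 = 0.50 |
| Half of passed failures lost (12.5, 25) | 37.5/987.5 = 3.8% | 921.5/934 = 98.7% | 25/53.5 = 46.7% | 946.5/987.5 = 95.8% | 25/37.5 = 0.67 |
| Half of flagged failures lost (25, 12.5) | 37.5/987.5 = 3.8% | 921.5/946.5 = 97.4% | 12.5/41 = 30.5% | 934/987.5 = 94.58% | 12.5/37.5 = 0.33 |

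The observed failure rate falls in every loss scenario. The predictive value of a normal test rises whenever passed failures are lost, and is unchanged if only flagged ones are. Sensitivity stays the same, rises or falls according to which failures are lost.

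**2. Range.** Take true failure of 2%, 5% or 10%, sensitivity of 0.3, 0.5 or 0.8, and equal loss of 30% to 50% of failed grafts.

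- Observed failure rate: 2% appears as 1.0-1.4%, 5% as 2.6-3.6%, 10% as 5.3-7.2%.
- Predictive value of a normal test: up by about 0.1 to 3.6 points.
- Agreement: up by about 0.1 to 3.2 points.

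**3. Worst-case bounds for a small study.** Assume 5 abnormal tests, 1 CTA failure after a normal test, and u patients with a normal test but no verification. The verified failure rate is 1/(normal − u). The bound (1 + u)/normal counts every unverified graft as occluded.

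- 150 patients, 145 normal, u = 4: 1/141 = 0.7%; bound 5/145 = 3.4%.
- 150 patients, 145 normal, u = 8: 1/137 = 0.7%; bound 9/145 = 6.2%.
- 100 patients, 95 normal, u = 5: 1/90 = 1.1%; bound 6/95 = 6.3%.

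These are limits under assumed inputs, not estimates of bias. If 2 of 4 unverified grafts had failed, the rate would be 3/145 = 2.1%.

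**The case against.** The strongest reply is that the protocol is silent rather than wrong. A single imaging reference, chosen for a stated reason, is a legitimate design. Denominators, missing reference results and bounding analyses are commonly left to a statistical analysis plan, and none is at hand. Most of that stands. A reader might infer that patients without a CTA are removed from the study or the denominator. The protocol does not say so; they are included at surgery, and how they are counted is left open.

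What the reply does not answer is the definition itself. What counts as a failed graft is set in the protocol, and it determines which records must be collected. Under that definition an occlusion proven by another route is not a failure.

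A reader might also infer that palpation's sensitivity must be inflated. The table shows otherwise: it rises only if the lost failures are mainly ones the test passed. That is plausible, because D.1 foresees revision of grafts in theatre, but it is not shown. The same mechanism cuts the other way. A flagged graft that is revised and then patent is not a CTA failure, so any example in which detected failures stay occluded until CTA conflicts with the reasoning behind it.

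Two further objections stand. The comparison of palpation with TTFM in section A needs no CTA. And the gap applies to TTFM as much as to palpation, so it does not clearly favour one over the other.

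**Conclusion.** The point holds in a limited form. CTA within 30 days is the sole reference, and a failure proven earlier by angiography, re-exploration or autopsy has no status under it. If such patients are lost, the patency rate and the predictive value of a normal palpation or TTFM result are probably overstated. This rests on failed grafts missing CTA more often than patent ones, which the protocol's own statements make plausible but do not establish; for the predictive value, some of the lost failures must also have had a normal test.

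The effect on sensitivity is of unknown sign. Under equal loss the predictive value of an abnormal test falls. The size cannot be derived from the document, and every figure above is conditional on assumed inputs. With few failures expected, one or two lost patients could visibly move the result.

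Nor does the gap by itself invalidate the D.1 conclusion, as a reader might conclude. D.1 states an expectation with two conditions and no threshold, not a decision rule.

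**What to change.** In B.1.1 and B.1.2.2, define LIMA-LAD failure to day 30 as occlusion on the study CTA, or occlusion shown by angiography, re-exploration or autopsy done for clinical reasons. Any failure proven by day 30 counts as not patent, whatever the order of the examinations. A graft patent on an early CTA and occluded at later re-exploration is thus a failure, and so is one found occluded, repaired and then patent on CTA.

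Report the number of patients without any verification, by palpation result and by TTFM result. Show the patency rate and the predictive value of a normal test with these patients counted first as patent and then as not patent. Present this as a sensitivity analysis, not as a gate on D.1.

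The cost is a short change to the protocol text, abstraction of records that already exist, and one table. No imaging, staff or patients are added and patient management does not change. The downside is a less uniform reference, because clinically triggered verification sits beside routine CTA. Reporting failures by route of verification keeps that visible. The figures may also be less favourable.

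### Kaplan-Meier is named for the primary endpoints, but the only postoperative data described are CTA readings within 30 days, which give patency status and not the date of occlusion

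*Protocol*

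**What the plan says.** The statistical methods in Protocol section B.1.2.2 b are one line: "Chi-square test, Student's t-test, Fisher's exact test, and Kaplan-Meier survival analysis for primary endpoints". Whether the closing phrase governs all four methods or only the last, Kaplan-Meier is assigned to the primary endpoints.

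The rest of the protocol shows what data there will be:

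- **Intraoperative.** Section B.1.2.2 a places both index tests in the operating room: "Bidirectional palpation and TTFM measurements will be conducted intraoperatively using standard techniques, posing no additional surgical risk".
- **Postoperative.** The end of section B.1.1 gives the only assessment: "Within the first 30 postoperative days, coronary CTA will evaluate patency of the LIMA and other grafts". The same scan also covers "graft-native vessel calibration, graft position, sternum healing, and lung parenchyma".
- **Aims.** Section A sets out to correlate palpation with TTFM and "to assess early postoperative outcomes by examining graft patency using coronary CT angiography". Section B.1.1 adds the "correlation between the bidirectional palpation test and TTFM with postoperative graft patency determined by coronary CT angiography".
- **Mortality and morbidity.** In section D.1 these appear as a hoped-for benefit: "This study is expected to reduce morbidity and mortality due to graft occlusion". They are not set up as endpoints with follow-up.

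**The concern.** Kaplan-Meier needs, for each patient, either an observed event time or a time up to which the patient is known to be event-free. A CTA gives the second for a patent graft but not the first for an occluded one: the occlusion happened on some unknown day up to the scan. With one scan per patient these are current-status data. If the scan date stands in for the event date, the steps of the curve mark when patients were imaged.

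Two results are at stake. The first is the reported occlusion percentage, which would depend on how scans are spread over the window and on how patent grafts are censored. The second is any comparison of curves by palpation or TTFM result, which would be distorted if the groups were scanned at different times.

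**Working it through.** The protocol states no sample size, event rate, scan-day distribution or censoring rule, so it has no figure to reproduce. The check has two parts.

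**1. Method against data**

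| Kaplan-Meier needs | What the protocol describes |
|---|---|
| Event date | None; a CTA reading of patent or occluded |
| Follow-up over time | CTA within 30 days; no fixed day, no repeat scan |
| A time-to-event endpoint | None; the aims concern correlation and CTA patency |

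The chi-square and Fisher's exact tests in the same sentence do suit a yes/no status. Kaplan-Meier is the item that does not fit.

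**2. Size, by scenario**

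Assumptions (none from the protocol): 100 patients, one scan each, true occlusion p = 5%, status independent of scan day, and scan date used as event or censoring date.

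*Scenario 1: scans uniform on days 1 to 30, patent grafts censored at scan.* On day j, a fraction 1/(31 − j) of those still at risk is scanned and p of these are occluded. The large-sample hazard is therefore p/(31 − j), and

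1 − KM(d) = 1 − ∏ (1 − p/k), with k running from 31 − d to 30.

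| Day | Formula, p = 5% | Simulated mean, n = 100 |
|---|---|---|
| 10 | 1.97% | 2.0% |
| 15 | 3.33% | 3.4% |
| 20 | 5.20% | 5.2% |
| 25 | 8.22% | 8.3% |
| 30 | 18.28% | 18.4% |

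At day 30 the formula gives 7.7% for a true 2% and 33.5% for a true 10%. For p = 5% the simulated day-30 mean is 17.3% with n = 50 and 18.1% with n = 150.

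*Scenario 2: scans on days 5 to 7, one third each day.* 1 − (1 − 0.05/3)(1 − 0.05/2)(1 − 0.05) = 1 − 0.9833 × 0.975 × 0.95 = 8.9%.

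*Scenario 3: all scans on one day.* 1 − (1 − 0.05) = 5.0%, no bias.

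*Scenario 4: scans as in scenario 1, patent grafts carried to day 30.* Nobody is censored early, so the curve ends at 5.0%. It reads 0.05 × 15/30 = 2.5% at day 15, although under these assumptions all occlusions are already present.

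*Scan dates on a continuous scale, uniform over days 5 to 30.* A separate simulation with n from 50 to 200 gives 20% to 26% at the last scan for a true 5%. The simple proportion stays at 5.0%.

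*Group comparison.* Two groups of 50, both with 5% true occlusion, log-rank test at the 5% level (the protocol names no log-rank test):

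| Scan windows | Log-rank false positives | Fisher's exact |
|---|---|---|
| Both days 1–30 | about 4% | below 1% |
| Days 1–15 v days 1–30 | about 24% | below 1% |

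*The alternative.* For 5 occluded of 100 scanned, the proportion is 5.0%, with exact 95% CI 1.6% to 11.3%, whatever the scan calendar.

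**The case against.** The strongest objection is that the endpoint is inferred. The protocol never lists its primary endpoints. Kaplan-Meier could be meant for death or reoperation, which have observed dates, and an unseen SAP might define such an endpoint. One scan per patient is also not stated. This stands as a limit on certainty. It does not remove the mismatch: section A says early outcomes are judged by CTA patency, section D.1 mentions mortality and reoperation only as expected benefit, and no follow-up that would yield event dates is described. A second scan would narrow the interval in which an occlusion occurred but still not date it.

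The figures are also open to challenge:

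- **The day-30 value is a thin tail.** With 100 patients over 30 days, only 100/30 ≈ 3.3 are at risk on the last day. The simulated day-30 estimate has a median of about 14.5% and a 5th-to-95th percentile range of roughly 3% to 45%. At day 20 the mean happens to be near the true 5%. This stands, so the 18% should be read with the whole curve.
- **Occlusions may not all be present by the first scan.** If they instead accrue evenly over 30 days, the curve gives about 1% at day 15 (true value 2.5%) and about 15% at day 30 (true value 5%). The numbers move, but the error at both ends remains.
- **Nothing suggests that scan timing differs by test result.** This is correct. The 24% shows what would happen if it did.

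Finally, the sentence is a generic list that already contains suitable tests, so the stated aims can still be answered. That keeps the point from being graver, but a method assigned to the primary endpoints should fit them.

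**Conclusion.** The concern holds. As written, the protocol assigns Kaplan-Meier to its primary endpoints and describes no data from which an event time could be observed. This is a misfit in the stated method, not a detail left to the SAP.

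The conclusion rests on two inferences: that the method is aimed at CTA patency, and that each patient has one scan. Both are the natural reading; neither is stated. Confidence is therefore medium.

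The direction of error is not fixed. Under the assumed 5% occlusion, the curve can be too low (3.3% at day 15), correct (one common scan day) or too high (about 9% for scans on days 5 to 7, about 18% at day 30 for scans over the full window). A group comparison is distorted only if scan timing differs between the groups. The point should be fixed, but it does not undermine the study's aims, none of which needs a survival curve.

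**What to change.** Reword the sentence in section B.1.2.2 b as follows:

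- Remove Kaplan-Meier for CTA patency.
- Analyse LIMA-LAD patency as a binary status: the number patent over the number scanned, with an exact 95% CI.
- Use that status as the reference for palpation and for TTFM, with the chi-square or Fisher's exact test already listed.
- Report the surgery-to-CTA interval descriptively.
- Keep Kaplan-Meier only if an endpoint with an observed event date is intended. In that case name the endpoint in the sentence, and state its time origin, follow-up and censoring.

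For CTA patency the cost is one sentence of protocol wording, with no extra patients or data. Keeping Kaplan-Meier for a dated endpoint would also require the protocol to describe how those dates are collected.

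### The methods named for the primary endpoints test association, mean difference or time to event; none estimates palpation–TTFM agreement or either test's performance against CTA patency

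*Protocol*

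**What the plan says.** The statistical section of the protocol (B.1.2.2 b) is one line: "Chi-square test, Student's t-test, Fisher's exact test, and Kaplan-Meier survival analysis for primary endpoints". No agreement measure, accuracy measure, paired comparison or correlation coefficient is named.

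The purpose is stated in four places:

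- Official Title: "Comparison of Bidirectional Palpation Test and Transit Time Flow Measurement for LIMA-LAD Graft Patency".
- Section A: "The aim of this study is to evaluate the correlation between the Bidirectional Palpation Test and TTFM measurements".
- Section B.1.1: "This study aims to assess the correlation between the bidirectional palpation test and TTFM with postoperative graft patency determined by coronary CT angiography".
- Section D.1: the method may be taken up more widely "if the bidirectional palpation test results are consistent with TTFM and early graft patency is confirmed via coronary CTA".

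Two further statements bear on timing. D.1 says "Revising the graft during surgery, if necessary, may prevent the risks and burden of reoperation", and B.1.1 says "Within the first 30 postoperative days, coronary CTA will evaluate patency of the LIMA and other grafts". The palpation result is described in B.1.1 as the pulse continuing or not, so it is binary. B.1.2.2 a has both tests done during the operation in a single cohort, so the two results are paired on the same graft.

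**The concern.** Chi-square and Fisher's exact test ask whether two classifications are related at all. Student's t-test asks whether mean flow differs between groups. Kaplan-Meier describes time to an event, and the protocol describes CTA within 30 days without a series of follow-up times, so patency has no clear event time. All are legitimate methods, and the first three fit the word correlation in the aims. None answers how often palpation and TTFM give the same result, or how often either is right when CTA is the reference.

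Two errors of interpretation can follow. A small p-value could be reported as showing consistency although palpation misses a large share of the grafts that TTFM calls abnormal. Conversely, with few abnormal grafts, many false alarms, or detected grafts that were revised and are then patent on CTA, the p-value may be non-significant although palpation found real problems. In neither case does the p-value give the rate at which an abnormal graft is missed, which anyone considering adoption needs to know.

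**Working it through.** The protocol gives no sample size, event count, specificity or revision rate, so there is no planned figure to reproduce. All counts below are assumed, with N = 100 grafts. They illustrate the argument and do not predict this trial's results.

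**1. Same p-value, opposite agreement.** Take palpation against TTFM, with rows and columns in the same category order.

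| Table | Raw agreement | Chance agreement | Kappa | Chi-square p | Fisher p |
|---|---|---|---|---|---|
| [[80, 5], [5, 10]] | 90/100 = 90% | 0.85×0.85 + 0.15×0.15 = 0.745 | (0.90 − 0.745)/0.255 = 0.61 | 1.2×10⁻⁹ | 4.0×10⁻⁷ |
| [[5, 80], [10, 5]] | 10/100 = 10% | 0.85×0.15 + 0.15×0.85 = 0.255 | (0.10 − 0.255)/0.745 = −0.21 | 1.2×10⁻⁹ | 4.0×10⁻⁷ |

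The tests cannot tell 90% agreement from 10%.

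**2. Same detection rate, different p-value.** Assume 6 of 100 grafts are abnormal on the comparator (TTFM or CTA), palpation misses 3 of them, and no graft is revised. Rows are comparator abnormal/normal; columns are palpation abnormal/normal.

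| False alarms | Table | Fisher p | Detected |
|---|---|---|---|
| 0 | [[3, 3], [0, 94]] | C(6,3)/C(100,3) = 20/161,700 = 0.00012 | 3/6 |
| 12 | [[3, 3], [12, 82]] | 0.042 | 3/6 |
| 13 | [[3, 3], [13, 81]] | 0.050 | 3/6 |
| 19 | [[3, 3], [19, 75]] | 0.12 | 3/6 |

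The exact (Clopper-Pearson) 95% CI for 3/6 is 12% to 88%. With 12 false alarms:

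- Correct on normal grafts: 82/94 = 87% (79% to 93%).
- Raw agreement: (3 + 82)/100 = 85%.
- Chance agreement: 0.06×0.15 + 0.94×0.85 = 0.808.
- Kappa: (0.85 − 0.808)/(1 − 0.808) = 0.22 (large-sample 95% CI about −0.04 to 0.48).

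So p falls below 0.05 while half the abnormal grafts are missed and the kappa interval includes zero.

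**3. Effect of revision on the comparison with CTA.** Start from the table with no false alarms. Suppose some of the 3 detected grafts are revised and are then patent on CTA, and the first palpation result is analysed. Each such graft moves from CTA-abnormal to CTA-patent and counts as a false positive.

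| Revised | Table | Fisher p | Apparent sensitivity |
|---|---|---|---|
| 0 | [[3, 3], [0, 94]] | 0.00012 | 3/6 = 50% |
| 1 | [[2, 3], [1, 94]] | (10×95 + 10)/161,700 = 0.0059 | 2/5 = 40% |
| 2 | [[1, 3], [2, 94]] | 1 − C(96,3)/C(100,3) = 0.12 | 1/4 = 25% |
| 3 | [[0, 3], [3, 94]] | 1.0 | 0/3 = 0% |

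With all 3 revised, apparent specificity is 94/97 = 97%. If the last result on the graft as left in place is used instead, and the revised grafts test normal, the table is [[0, 3], [0, 97]]. Specificity returns to 97/97, but sensitivity stays 0/3 (exact 95% CI 0% to 71%). CTA cannot verify a result taken on a graft that was later revised. Choosing the later result removes the false positives but does not recover the detections.

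**The case against.** The strongest reply is that both explicit aims, in A and B.1.1, speak of correlation. Chi-square and Fisher address association, and a t-test can compare flow by palpation result. D.1 describes expected impact and sets neither an endpoint nor a decision rule. The one-line list does not forbid descriptive proportions, and sensitivity, specificity, kappa and a TTFM cut-off are often left to a statistical analysis plan, which is not at hand here. The revision text in D.1 is a general statement of benefit: nothing says how many grafts will be revised, whether measurements are repeated, or which result is analysed. The counts are assumed, and the 50% detection rate is an input.

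Much of this is fair as to scope. The named tests are not invalid, the revision point is conditional on revisions occurring, and the figures demonstrate a principle without measuring this trial. The core stands. The protocol itself assigns these methods to the primary endpoints. The title and the B.1.1 aim ask how two tests perform for patency with CTA as the reference, and D.1 draws on consistency between them. A later plan could add the right measures, but the line as written would still name primary methods that do not estimate what the study sets out to show.

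**Conclusion.** The concern holds and should be fixed. The stated primary methods do not match the stated purpose: they cannot quantify palpation–TTFM agreement or either test's performance against CTA. Under the assumed 100 grafts with 3 of 6 abnormal grafts missed, Fisher's p runs from 0.00012 to 0.12 as false alarms go from 0 to 19, with detection fixed at 50%. Revision of 0 to 3 of the detected grafts moves p from 0.00012 to 1.0 and apparent sensitivity from 50% to 0%. The size in this trial is unknown because the protocol gives none of the inputs. That association does not establish agreement does not depend on the assumed counts. The data remain usable, since an ordinary cross-tabulation yields the estimates needed.

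**What to change.** Restate the main analysis in B.1.2.2 b:

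1. **Agreement of palpation with TTFM.** Use the pair of results recorded at the same point before any revision, with TTFM classed abnormal or normal by a definition fixed before analysis. Report the share of TTFM-abnormal grafts that are palpation-abnormal and the share of TTFM-normal grafts that are palpation-normal, each with an exact 95% CI. Kappa can supplement these.
2. **Performance against CTA.** Report sensitivity and specificity of palpation, and of TTFM, for LIMA-LAD patency with exact 95% CIs. Pair CTA with the last measurement on the graft as left in place, and label the result so. Because the title promises a comparison, a paired difference between the two tests on the same grafts would be a useful addition.
3. **Revised grafts.** Report their number and their pre-revision palpation and TTFM results separately, since CTA cannot verify these. This is an analysis rule only and sets no criterion for revising.
4. **Named tests.** Keep chi-square, Fisher and the t-test as supporting association analyses. Drop Kaplan-Meier for patency unless an endpoint with an event time is defined.
5. **Wording.** Rest any claim of consistency under D.1 on the estimates and their intervals, and not on a p-value.

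The cost is statistical wording, one TTFM definition and one rule for revised grafts, with no extra patients or scans. It needs a record of whether each graft was revised and which results came before and after. The start date of April 15, 2024 and 6-month duration (C.1, C.2), set against the document date of 11.10.2024, suggest much of the data may already be collected, so item 1 may be limited to grafts with such records. Intervals will be wide if few grafts are abnormal or non-patent, dichotomising TTFM loses some flow information, and item 2 describes grafts as left in place rather than palpation's detection rate before revision.
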